Appendix B: Continued-Access Period Assessments

| | Continued-Access Treatment Visits ±3 Days | Continued-Access Follow-Up Visits 30 days (±7 days) after the last dose of study treatment |
|----------------------------------|--|---|
| Treatment: AM0010 | X | |
| Adverse event | X | X |
| Survival assessment ^a | X | X |

^a Every 12 weeks

CCI

CCI

The image shows the logo for CCI (Clinical Care Innovations). It consists of the letters 'C', 'C', and 'I' in a bold, orange, sans-serif font. The letters are positioned on a solid black rectangular background that covers most of the page.

CCI

CCI

The image shows the letters 'CCI' in a large, bold, orange font. The letters are set against a solid black rectangular background that covers most of the page. The 'C' is a simple, rounded shape. The second 'C' is identical to the first. The 'I' is a vertical bar with a slightly wider top and bottom, also in the same orange color.

The image shows the letters 'CCI' in a large, bold, orange font. The letters are set against a solid black rectangular background that covers most of the page. The 'C's are stylized with a slight gap at the bottom, and the 'I' is a simple vertical bar.

CCI

Appendix D: Dose Modification Tables for FOLFOX – FOLFOX/AM0010

| Adverse Event | Occ. | Oxaliplatin | 5-Fluorouracil | AM0010 |
|---|-----------------|--|---|---|
| Hematological AEs | | | | |
| Grades 3-4 anemia or Grades 3-4 thrombocytopenia | 1 st | Hold until G1 or baseline Reintroduce at dose level –1 | Hold until G1 or baseline Reintroduce at dose level –1 | Hold until G1 or baseline Reintroduce to Dose Level –1 |
| | 2 nd | Hold until G1 or baseline Reintroduce at dose level –2 | Hold until G1 or baseline Reintroduce at dose level –2 | Hold until G1 or baseline Reintroduce to Dose Level –2 |
| | 3 rd | Hold until G1 or baseline No change in dose | Hold until G1 or baseline No change in dose | Hold until G1 or baseline No change in dose |
| Grades 3-4 neutropenia or Grades 3-4 leukopenia or Grades 3-4 neutropenic fever | 1 st | Hold until G1 or baseline Reintroduce at dose level –1 | Hold until G1 or baseline Reintroduce at dose level –1 | Continue dosing; no change in dose schedule |
| | 2 nd | Hold until G1 or baseline Reintroduce at dose level –2 | Hold until G1 or baseline Reintroduce at dose level –2 | |
| Hemolytic uremic syndrome (HUS) ³ | 1 st | Discontinue | Hold until G1 or baseline No change in dose | Hold until G1 or baseline No change in dose |
| Non-hematological AEs | | | | |
| Grade 3 Diarrhea | | Hold until G1 or baseline No change in dose level | Hold until G1 or baseline Reintroduce at dose level –1 | Continue dosing; no change in dose schedule |
| Grade 4 Diarrhea | | Hold until G1 or baseline Reintroduce at dose level –1 | Hold until G1 or baseline Reintroduce at dose level –1 | |
| Cough ≥Grade 3 Dyspnea ≥Grade 3 Hypoxia ≥Grade 3 Pneumonitis ≥Grade 3 | | Hold oxaliplatin until interstitial lung disease is ruled out. If interstitial lung disease, discontinue oxaliplatin | Hold until G1 or baseline No change in dose | Hold until G1 or baseline No change in dose schedule |
| Grade 3 Fatigue | | Hold until G1 or baseline No change in dose level | Hold until G1 or baseline No change in dose level | Hold until G1 or baseline No change in dose schedule |
| Other non- hematological AEs ^{3,4} | | Hold until G1 or baseline | | No change in dose schedule |

| | | | |
|--|--|---|--|
| | | Reduce offending agent by 1 dose level ¹ | |
|--|--|---|--|

Appendix D Dose Modification Tables for FOLFOX – FOLFOX / AM0010 (Cont'd)

| Adverse Event | Occ. | Oxaliplatin | 5-Fluorouracil | AM0010 |
|---|------|---|-------------------|--|
| Non-hematological AEs | | | | |
| Hypomagnesemia | | Hold until G1 or baseline No change in dose level | | |
| Neurological AEs | | | | |
| Persistent ⁵ Grade 2 paresthesias/ dysesthesias ⁶ | | Reduce dose to level -1 | No change in dose | Continue dosing; no change in dose schedule |
| Grade 3 paresthesias/ dysesthesias ⁶ | | Hold until G1 or baseline Discontinue, if persistent ⁵ | | |
| Grade 4 paresthesias/ dysesthesias ⁶ | | Discontinue | | |
| Grade 2 = moderate (also recommended is administration of benzodiazepine and patient education. Management of patient if ≥Grade 2 laryngeal dysesthesias occurs while treatment is being administered.) Grade 3 = severe | | Stop oxaliplatin infusion. Administer benzodiazepine and give patient reassurance. At the discretion of the Investigator, the infusion can be restarted at 1/3 the original rate of infusion. Continue 5-FU | | Continue dosing; no change in dose schedule |

¹ If an AE is believed likely to be due to only 1 of the drugs, it is permissible to decrease dose of that drug only.

² Recommended evaluation of suspected HUS: Evaluation should include CBC differential, platelets, PT, PTT, fibrinogen, FDP, Anti thrombin III, Von Willebrand factor, anti-nuclear antibody, rheumatoid factor, Compliment Cascade C3, C4, and CH50, anti-platelet antibodies, platelet-associated IgG, and circulating immune complexes. Renal evaluation should include creatinine, BUN, and urinalysis with microscopic examination. Other laboratory and hematologic evaluations as appropriate should also be obtained, including peripheral blood smear and free hemoglobin.

³ Exceptions: fatigue, anorexia, nausea/vomiting if can be controlled by antiemetic, and viral infections.

⁴ Dose modifications for other non-hematologic AEs at the start of subsequent courses of therapy, and at time of retreatment are also based on NCI CTCAE v4.03 criteria.

⁵ Not resolved by the beginning of the next cycle.

⁶ May be cold-induced.

Leucovorin doses may be adjusted per institutional guidelines in the event of a supply shortage.

Dose Reduction Levels^a for FOLFOX

| Drug | Dose Level | | |
|---|------------------------|------------------------|------------------------|
| | Starting Dose | -1 | -2 ^b |
| Oxaliplatin | 85 mg/m ² | 65 mg/m ² | 50 mg/m ² |
| 5-FU bolus | 400 mg/m ² | Omit | Omit |
| 5-FU continuous infusion over 46–48 hours | 2400 mg/m ² | 1900 mg/m ² | 1500 mg/m ² |
| dl-Leucovorin/l-Leucovorin ^c | 400 mg/m ² | 100% | 100% |

^a If an AE is believed likely to be due to 1 drug, it is permissible to decrease dose of that drug only.

^b Further dose levels (-3, -4, etc.) will be 20% dose reductions from the previous level for oxaliplatin and 5-FU continuous infusion. In addition, the bolus dose of 5-FU will continue to be omitted, and the leucovorin dose will remain unadjusted (100%).

^c Dosing of leucovorin will remain fixed at 100% of recommended dose. Non-racemic L-leucovorin dose at 200 mg/m².

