- Neutropenia and neutropenic fever Grades 3–4 with ANC $<1,000/\text{mm}^3$: delay treatment with FOLFOX until ANC returns to $>1,000/\text{mm}^3$. Re-introduction of FOLFOX should occur at dose level –1. If on a subsequent cycle these toxicities recur, FOLFOX is reduced to dose level –2 after the first recurrence. AM0010 dosing will continue without interruption.

Non-Hematologic Toxicity Dose Schedule Adjustment Requirements (graded according to the NCI CTCAE v4.03, [Appendix G](#)):

- \geq Grade 3 fatigue, elevations in AST, ALT, alkaline phosphatase, or bilirubin require dose interruption and delay in subsequent therapy until recovered to \leq Grade 1 or pre-therapy baseline. Re-introduction of all agents at the previous dose level.
- \geq Grade 3 GI AEs such as diarrhea, nausea, vomiting, abdominal pain, and bloating require a delay in subsequent therapy until recovered to \leq Grade 1 or pre-therapy baseline. Re-introduction: Reduce offending agent by 1 dose level. Keep other agents unchanged.
- Other non-hematologic toxicities with an impact on organ function of \geq Grade 3 require dose reduction. Hold treatment for the offending agent (or all agents, see [Table 11](#)), delay in subsequent therapy until recovered to \leq Grade 1 or pre-therapy baseline. Re-introduction: Reduce offending agent by 1 dose level. Keep other agents unchanged.
If AM0010 is suspected to be one of the offending agents, reintroduction will be at the original dose after the first occurrence. If on a subsequent cycle these toxicities recur, the AM0010 treatment schedule will be decreased to 80%. Upon second recurrence of Grade 3 or 4 AE, the AM0010 dose will be decreased to 60%. This will be accomplished by altering the dose schedule from 5 days on and 2 days off to 4 days on and 3 days off (80%), and 3 days on 4 days off (60%), respectively. See below.
- It is common for oxaliplatin to cause Grade 3 or 4 neuropathy by 4 months of therapy. On both treatment arms following the dose modification in [Table 11](#) for neuropathy, if oxaliplatin needs to be discontinued, continue therapy with 5-FU/LV.

Table 11: Dose Interruption, Reduction, and Dose Schedule Modifications

| Adverse Event | Occurrence | Oxaliplatin | 5-Fluorouracil | AM0010 |
|---|-----------------|--|---|---|
| Hematological AEs | | | | |

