| Grades 3-4 Anemia or Grades 3-4 Thrombocytopenia | 1 st | Hold until G1 or baseline Reintroduce at dose level –1 | Hold until G1 or baseline Reintroduce at dose level –1 | Hold until G1 or baseline Reintroduce to Dose Level –1 |
| | 2 nd | Hold until G1 or baseline Reintroduce at dose level –2 | Hold until G1 or baseline Reintroduce at dose level –2 | Hold until G1 or baseline reintroduce to Dose Level –2 |
| | 3 rd | Hold until G1 or baseline No change in dose | Hold until G1 or baseline No change in dose | Hold until G1 or baseline No change in dose |
| Grades 3–4 neutropenia or Grades 3–4 leukopenia or Grades 3–4 neutropenic fever | 1 st | Hold until G1 or baseline Reintroduce at dose level –1 | Hold until G1 or baseline Reintroduce at dose level –1 | Continue dosing; no change in dose schedule |
| | 2 nd | Hold until G1 or baseline Reintroduce at dose level –2 | Hold until G1 or baseline Reintroduce at dose level –2 | |
| Hemolytic uremic syndrome (HUS) ² | 1 st | Discontinue | Hold until G1 or baseline No change in dose | Hold until G1 or baseline No change in dose |
| Non-hematological AEs | | | | |
| Grade 3 Diarrhea | | Hold until G1 or baseline No change in dose level | Hold until G1 or baseline Reintroduce at dose level –1 | Continue dosing; no change in dose schedule |
| Grade 4 Diarrhea | | Hold until G1 or baseline Reintroduce at dose level –1 | Hold until G1 or baseline Reintroduce at dose level –1 | |
| Cough ≥Grade 3 Dyspnea ≥Grade 3 Hypoxia ≥Grade 3 Pneumonitis ≥Grade 3 | | Hold oxaliplatin until interstitial lung disease is ruled out. If interstitial lung disease, discontinue oxaliplatin. | Hold until G1 or baseline No change in dose | Hold until G1 or baseline No change in dose schedule |
| Grade 3 Fatigue | | Hold until G1 or baseline No change in dose level | Hold until G1 or baseline No change in dose level | Hold until G1 or baseline No change in dose schedule |

Table 11: Dose Interruption, Reduction, and Dose Schedule Modifications

| Adverse Event | Occurrence | Oxaliplatin | 5-Fluorouracil | AM0010 |
|--|------------|--|-------------------|---|
| Non-hematological AEs | | | | |
| Other G3/G4 non-hematological AEs ^{3,4} | | Hold until G1 or baseline Reduce offending agent by 1 dose level ¹ | | No change in dose schedule |
| Hypomagnesemia | | Hold until G1 or baseline No change in dose level | | |
| Neurological AEs | | | | |

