| Persistent ⁵ Grade 2 Paresthesias/ Dysesthesias ⁶ | | Reduce dose to level –1 | No change in dose | Continue dosing; no change in dose schedule |
| Grade 3 Paresthesias/ dysesthesias ⁶ Dysesthesias ⁶ | | Hold until G1 or baseline Discontinue, if persistent ⁵ | | |
| Grade 4 Paresthesias/ dysesthesias ⁶ Dysesthesias ⁶ | | Discontinue | | |
| Grade 2 = moderate (also recommended is administration of benzodiazepine and patient education. Management of patient if ≥ Grade 2 laryngeal dysesthesias occurs while treatment is being administered.) Grade 3 = severe | | Stop oxaliplatin infusion. Administer benzodiazepine and give patient reassurance. At the discretion of the Investigator, the infusion can be restarted at 1/3 the original rate of infusion. Continue 5-FU | | Continue dosing; no change in dose schedule |

¹ If an AE is believed likely to be due to only 1 of the drugs, it is permissible to decrease dose of that drug only.² Recommended evaluation of suspected HUS: Evaluation should include complete blood count (CBC) differential, platelets, PT, PTT, fibrinogen, FDP, Anti thrombin III, Von Willebrand factor, anti-nuclear antibody, rheumatoid factor, Compliment Cascade C3, C4, and CH50, anti-platelet antibodies, platelet-associated IgG, and circulating immune complexes. Renal evaluation should include creatinine, BUN, and urinalysis. Other laboratory and hematologic evaluations as appropriate should also be obtained, including peripheral blood smear and free hemoglobin.³ Exceptions: fatigue, anorexia, nausea/vomiting if can be controlled by antiemetics, and viral infections.⁴ Dose modifications for other non-hematologic adverse events at the start of subsequent courses of therapy, and at time of retreatment are also based on NCI CTCAE v4.03 criteria.⁵ Not resolved by the beginning of the next cycle.⁶ May be cold-induced.

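### Section 5.2 and the dose-modification tables conflict on FOLFOX restart after Grade 3 or higher liver-test rises and antiemetic-controlled nausea or vomiting

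*Protocol*

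**What the plan says.** FOLFOX dose changes are described in three places in the protocol: the bullets of Section 5.2, Table 11 in the same section, and Appendix D, which largely repeats Table 11.

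**Section 5.2 text.** One bullet groups Grade 3 or higher fatigue with liver tests: "elevations in AST, ALT, alkaline phosphatase, or bilirubin require dose interruption and delay in subsequent therapy until recovered to" Grade 1 or baseline. It ends "Re-introduction of all agents at the previous dose level". The next bullet covers the gut: Grade 3 or higher "GI AEs such as diarrhea, nausea, vomiting, abdominal pain, and bloating require a delay in subsequent therapy until recovered to" Grade 1 or baseline, followed by "Re-introduction: Reduce offending agent by 1 dose level. Keep other agents unchanged". It makes no allowance for antiemetic control.

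**Table 11 and Appendix D.** Neither has a row for liver tests or for nausea and vomiting. Both have a residual row for other non-hematological events, which in Table 11 reads "Hold until G1 or baseline Reduce offending agent by 1 dose level". Footnote 3 to that row lists what is left out of it. Appendix D has "Exceptions: fatigue, anorexia, nausea/vomiting if can be controlled by antiemetic, and viral infections", and Table 11 has the same list. Both tables give Grade 3 fatigue its own row with no dose change. For Grade 4 diarrhea, both tables hold oxaliplatin and 5-FU and bring each back at level -1.

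**Standing of each source.** The 5.2 bullets are headed as requirements. Section 5.2.1 says that recommended FOLFOX reductions rest on Table 11 and Appendix D. Footnote 1 of the tables and footnote a of Table 12 permit lowering only the drug thought responsible.

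**The concern.** A site treating one of these two events can find a reduced restart dose in one place and an unreduced one in another. FOLFOX is both the control regimen and the backbone of Arm 1, so the ambiguity touches both arms. Patients with liver metastases may enter with AST, ALT or alkaline phosphatase up to 5 x ULN (Section 3.1.1), so the liver-test rule may well be consulted.

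What is at stake is uniform dosing across sites and the meaning of two SAP summaries: dose reductions by component and reason (SAP 10.1.4.1) and relative dose intensity (SAP 10.1.1). If sites follow different pages, these tables describe a mixture of two rules. It would also be unclear whether a given restart dose departed from the protocol.

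**Working it through.** **Step 1. Set the sources side by side for oxaliplatin and 5-FU.**

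| Event | Section 5.2 text | Table 11 and Appendix D | Relation |
|---|---|---|---|
| Liver tests, Grade 3 or higher | Hold; restart all agents at previous level | No own row, not in footnote 3, so residual row: hold; offending agent down one level | No reduction versus reduction |
| Nausea/vomiting, Grade 3 or higher, controllable by antiemetics | Delay; offending agent down one level | No own row; footnote 3 takes it out of the hold-and-reduce row | Reduction versus no stated reduction |
| Diarrhea, Grade 4 | Delay; offending agent down one level, others unchanged | Hold; oxaliplatin and 5-FU both to level -1 | Both reduce; scope differs |

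The first two rows run in opposite directions: the tables are stricter for liver tests and the text is stricter for nausea and vomiting. A site taking the stricter instruction each time would follow the tables for one event and the text for the other.

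**Step 2. Check the liver-test inference.** The tables never name liver tests, so their place in the residual row is inferred. Fatigue is a useful comparison because it shares the 5.2 bullet with liver tests. It was carried into the tables twice, with its own no-change row and a place in footnote 3. Liver tests were carried into neither.

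**Step 3. Size the gap for a first event from the starting dose (Protocol Table 12).**

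- Oxaliplatin: starting 85 mg/m², level -1 is 65 mg/m². 65/85 = 76.5%, a drop of 20/85 = 23.5%.
- 5-FU starting total: 400 (bolus) + 2400 (infusion) = 2800 mg/m² per cycle. This reproduces the planned dose intensity in SAP Table JZGB.10.1.
- 5-FU at level -1: bolus omitted, infusion 1900 mg/m². 1900/2800 = 67.9%, a drop of 900/2800 = 32.1%.

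The other source gives 100% for the same drug. Only the offending agent is reduced, so the two percentages need not both apply to one patient. They hold for the first step only; from level -1 to level -2, 5-FU goes to 1500/1900 = 78.9% of its previous dose.

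**Step 4. Relate this to the SAP.** For the cycles after the event, 76.5% and 67.9% both lie in the SAP band from 60% to below 80%. A patient's overall relative dose intensity also depends on how many cycles come before and after, so this does not place whole patients in that band.

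**The case against.** The best case against the point has three parts.

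1. **Liver tests.** Section 5.2 has its own bullet for other non-hematologic toxicities. It comes after the liver and gut bullets, refers to Table 11 and uses the same instruction as the residual row. On that reading, *other* means events not already named in the text, and the liver bullet only supplements the tables. This is a possible reading, and it confirms that the conflict is inferred. It does not remove it: each table defines its residual row by its own rows and exceptions, and Section 5.2.1 sends the reader to those tables for FOLFOX reductions.

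2. **Nausea and vomiting.** Leaving a row is not the same as needing no action. Fatigue is in the same exception list and is still held under its own row. That is fair as far as it goes, but nausea and vomiting have no other row. If the 5.2 bullet applied regardless, the antiemetic condition would make no difference to the dose.

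3. **Precedence.** Section 5.2.1 does point to Table 11 and Appendix D. It calls the reductions recommended, though, while the 5.2 bullets are headed as requirements. Nothing says what to do when they differ.

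One part of the opposing case stands in full. A reader might infer that Grade 4 diarrhea is a third contradiction. It is not. Both sources hold and reduce, and they differ only on whether a non-offending FOLFOX drug is also lowered. The footnotes allowing reduction of one drug only largely bridge that. Footnote 1 is marked only on the residual row, but its wording is general and Table 12 repeats it.

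**Conclusion.** The conflict holds for two events: Grade 3 or higher liver-test rises, and Grade 3 or higher nausea or vomiting that antiemetics can control. Grade 4 diarrhea is a lesser difference in scope. Per affected patient, for a first event from the starting dose, the offending drug restarts at 100% or at 76.5% (oxaliplatin) or 67.9% (total 5-FU), depending on the page used. This rests on reading the residual row as covering every non-hematological event without its own row or exception.

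Three stronger conclusions might be inferred, and the documents do not support them:

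- **A count of affected patients.** No event rates are given, so the number is unknown.
- **A choice of page that follows the known arm.** The trial is open-label, so this is conceivable, but the same text governs both arms and nothing shows it.
- **Damage to the main analyses.** The SAP exposure tables use actual doses and remain computable. The listed per-protocol exclusions, which the SAP says are not exhaustive, include no dose-modification departure. No effect on the intent-to-treat overall survival analysis, its alpha, power or sample size is claimed.

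This is a wording inconsistency in instructions that set the FOLFOX dose in both arms. It is worth correcting because the correction is cheap.

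**What to change.** Reconcile the Section 5.2 text, Table 11 and Appendix D so that liver-test elevations and antiemetic-controlled nausea or vomiting each carry one FOLFOX instruction, stated the same way in all three places. Align the Grade 4 diarrhea wording on whether a non-offending drug is also lowered. Add one sentence saying which source governs if they differ. Which rule is right is for the sponsor's clinical team to decide; this review takes no position on it.

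While the tables are open, correct two nearby mismatches. Table 11 limits the residual row to Grade 3 or 4 events and Appendix D does not. Appendix D also marks hemolytic uremic syndrome with footnote 3 (the exceptions), where Table 11 uses footnote 2 (the work-up).

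The cost is wording in a clarification or amendment and a memo to sites. No added data or patients are needed.

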Appendix E: ECOG Performance Status*

| Grade | ECOG |
|--------------|---|
| 0 | Fully active, able to carry on all pre-disease performance without restriction |
| 1 | Restricted in physically strenuous activity but ambulatory and able to carry out work of a light or sedentary nature, eg, light house work, office work |
| 2 | Ambulatory and capable of all self-care but unable to carry out any work activities. Up and about more than 50% of waking hours |
| 3 | Capable of only limited self-care, confined to bed or chair more than 50% of waking hours |
| 4 | Completely disabled. Cannot carry on any self-care. Totally confined to bed or chair |
| 5 | Dead |

*As published in ([Oken, Creech et al., 1982](#)).

Appendix G: NCI CTCAE v4.03

https://ctep.cancer.gov/protocolDevelopment/electronic_applications/docs/CTCAE_4.03.xlsx

Appendix H: Birth Control Methods That May Be Considered Highly Effective

Methods that can achieve a failure rate of less than 1% per year when used consistently and correctly are considered as highly effective birth control methods. Such methods include:

- combined (estrogen and progestogen containing) hormonal contraception associated with inhibition of ovulation 1:
 - oral
 - intravaginal
 - transdermal

- progestogen-only hormonal contraception associated with inhibition of ovulation 1:
 - oral
 - injectable
 - implantable
 - intrauterine device (IUD)
 - intrauterine hormone-releasing system (IUS)
 - bilateral tubal occlusion
 - vasectomized partner
 - sexual abstinence

Guidance on the acceptable contraception methods can be found here:

http://www.hma.eu/fileadmin/dateien/Human_Medicines/01-About_HMA/Working_Groups/CTFG/2014_09_HMA_CTFG_Contraception.pdf.

Appendix I: Hepatic Monitoring Tests for Treatment-Emergent Abnormality

Selected tests may be obtained in the event of a treatment-emergent hepatic abnormality and may be required in follow-up with patients in consultation with the Lilly CRP.

Hepatic Monitoring Tests

| | |
|---------------------------------------|--|
| Hepatic Hematology^a | Haptoglobin^a |
| Hemoglobin (HGB) | |
| Hematocrit (HCT) | Hepatic Coagulation^a |
| Erythrocytes (RBC) | Prothrombin time (PT) |
| Leukocytes (WBC) | Prothrombin time, INR |
| Neutrophils ^b | |
| Lymphocytes | Hepatic Serologies^{a,c} |
| Monocytes | Hepatitis A antibody, total |
| Eosinophils | Hepatitis A antibody, IgM |
| Basophils | Hepatitis B surface antigen |
| Platelets (PLT) | Hepatitis B surface antibody |
| | Hepatitis B Core antibody |
| Hepatic Chemistry^a | Hepatitis C antibody |
| Total bilirubin | Hepatitis E antibody, IgG |
| Direct bilirubin | Hepatitis E antibody, IgM |
| Alkaline phosphatase | |
| Alanine aminotransferase (ALT) | Recommended Autoimmune Serology |
| Aspartate aminotransferase (AST) | Anti-nuclear antibody ^a |
| Gamma-glutamyl transferase (GGT) | Anti-smooth muscle antibody ^a |
| Creatine phosphokinase (CPK) | Anti-actin antibody ^a |

Abbreviations: CRF = case report form; IgG = immunoglobulin G; IgM = immunoglobulin M;

INR = international normalized ratio; RBC = red blood cells; WBC = white blood cells.

- ^a Assayed by Lilly-designated laboratory.
- ^b Neutrophils reported by automated differential hematology instruments include both segmented and band forms. Whenever a manual differential is needed to report the neutrophils, the segmented and band forms should be added together and recorded on the CRF, unless the CRF specifically provides an entry field for bands.
- ^c Confirmation dependent on regulatory requirements and/or testing availability.

Leo Document ID = a1259399-3030-48b6-b429-37b771509515

Approver: PPD [REDACTED]
Approval Date & Time: 03-Oct-2018 17:43:54 GMT
Signature meaning: Approved

Approver: PPD [REDACTED]
Approval Date & Time: 05-Oct-2018 02:13:54 GMT
Signature meaning: Approved
